## Appendix 4      **Eastern Cooperative Oncology Group (ECOG) Performance Status**

| Grade | Description                                                                                                                                                   |
|-------|---------------------------------------------------------------------------------------------------------------------------------------------------------------|
| 0     | Fully active, able to carry on all pre-disease performance without restriction.                                                                               |
| 1     | Restricted in physically strenuous activity, but ambulatory and able to carry out work of a light or sedentary nature (e.g., light house work or office work) |
| 2     | Ambulatory and capable of all self-care, but unable to carry out any work activities. Up and about more than 50% of waking hours.                             |
| 3     | Capable of only limited self-care, confined to bed or chair more than 50% of waking hours.                                                                    |
| 4     | Completely disabled. Cannot carry-on any self-care. Totally confined to bed or chair.                                                                         |
| 5     | Dead                                                                                                                                                          |

## Appendix 5        RECIST v1.1 Guidelines

Adapted from Eisenhauer 2009 ([22](#)).

All participants will be required to have at least 1 measurable lesion to be considered as having measurable disease at baseline for the determination of eligibility for this study. Measurable lesions are defined below.

### 1            Measurability of Tumor at Baseline

#### 1.1        Definitions

At baseline, tumor lesions/lymph nodes will be categorized measurable or non-measurable as follows:

##### 1.1.1        Measurable

*Tumor lesions:* Must be accurately measured in at least one dimension (*longest* diameter in the plane of measurement is to be recorded) with a *minimum* size of:

- 10 mm by CT scan (CT scan slice thickness no greater than 5 mm).
- 10 mm caliper measurement by clinical exam (lesions which cannot be accurately measured with calipers should be recorded as non-measurable).
- 20 mm by chest X-ray.

*Malignant lymph nodes:* To be considered pathologically enlarged and measurable, a lymph node must be  $\geq 15$  mm in *short* axis when assessed by CT scan (CT scan slice thickness recommended to be no greater than 5 mm). At baseline and in follow-up, only the *short* axis will be measured and followed. See also notes below on 'Baseline documentation of target and non-target lesions' for information on lymph node measurement.

##### 1.1.2        Non-measurable

All other lesions, including small lesions (longest diameter  $< 10$  mm or pathological lymph nodes with  $\geq 10$  to  $< 15$  mm short axis) as well as truly non-measurable lesions. Lesions considered truly non-measurable include leptomeningeal disease, ascites, pleural or pericardial effusion, inflammatory breast disease, lymphangitic involvement of skin or lung, abdominal masses/abdominal organomegaly identified by physical exam that is not measurable by reproducible imaging techniques.

##### 1.1.3        Special considerations regarding lesion measurability

Bone lesions, cystic lesions, and lesions previously treated with local therapy require particular comment:

Bone lesions:

- Bone scan, PET scan or plain films are not considered adequate imaging techniques to measure bone lesions. However, these techniques can be used to confirm the presence or disappearance of bone lesions.
- Lytic bone lesions or mixed lytic-blastic lesions, *with identifiable soft tissue components*, that can be evaluated by cross sectional imaging techniques such as CT or MRI can be considered as measurable lesions if the *soft tissue component* meets the definition of measurability described above.
- Blastic bone lesions are non-measurable.

Cystic lesions:

- Lesions that meet the criteria for radiographically defined simple cysts should not be considered as malignant lesions (neither measurable nor non-measurable) since they are, by definition, simple cysts.
- ‘Cystic lesions’ thought to represent cystic metastases can be considered as measurable lesions, if they meet the definition of measurability described above. However, if non-cystic lesions are present in the same participant, these are preferred for selection as target lesions.

Lesions with prior local treatment:

- Tumor lesions situated in a previously irradiated area, or in an area subjected to other loco-regional therapy, are not considered measurable unless there has been demonstrated progression in the lesion prior to study enrollment.

## 1.2 Specifications by methods of measurements

### 1.2.1 Measurement of lesions

All measurements should be recorded in metric notation, using calipers if clinically assessed. All baseline evaluations should be performed as close as possible to the treatment start and never more than 4 weeks before the beginning of the treatment.

### 1.2.2 Method of assessment

The same method of assessment and the same technique should be used to characterize each identified and reported lesion at baseline and during follow-up. Imaging based evaluation should always be done rather than clinical examination unless the lesions(s) being followed cannot be imaged but are assessable by clinical exam.

*Clinical lesions:* Clinical lesions will only be considered measurable when they are superficial and  $\geq 10$  mm diameter as assessed using calipers (e.g., skin nodules). For the case of skin

lesions, documentation by color photography including a ruler to estimate the size of the lesion is suggested. As noted above, when lesions can be evaluated by both clinical exam and imaging, imaging evaluation should be undertaken since it is more objective and may also be reviewed at the end of the study.

*Chest X-ray:* Chest CT is preferred over chest X-ray, particularly when progression is an important endpoint, since CT is more sensitive than X-ray, particularly in identifying new lesions. However, lesions on chest X-ray may be considered measurable if they are clearly defined and surrounded by aerated lung.

*CT, MRI:* CT is the best currently available and reproducible method to measure lesions selected for response assessment. This guideline has defined measurability of lesions on CT scan based on the assumption that CT slice thickness is 5 mm or less. When CT scans have slice thickness greater than 5 mm, the minimum size for a measurable lesion should be twice the slice thickness. MRI is also acceptable in certain situations (e.g., for body scans).

*Ultrasound:* Ultrasound is not useful in assessment of lesion size and should not be used as a method of measurement. Ultrasound examinations cannot be reproduced in their entirety for independent review at a later date and, because they are operator dependent, it cannot be guaranteed that the same technique and measurements will be taken from one assessment to the next. If new lesions are identified by ultrasound in the course of the study, confirmation by CT or MRI is advised. If there is concern about radiation exposure at CT, MRI may be used instead of CT in selected instances.

*Endoscopy, laparoscopy:* The utilization of these techniques for objective tumor evaluation is not advised.

*Tumor markers:* Tumor markers *alone* cannot be used to assess *objective* tumor response.

## **2 Tumor Response Evaluation**

### **2.1 Assessment of overall tumor burden and measurable disease**

To assess objective response or future progression, it is necessary to estimate the *overall tumor burden at baseline* and use this as a comparator for subsequent measurements. Only patients with measurable disease at baseline should be included. Measurable disease is defined by the presence of at least one measurable lesion (as detailed above).

### **2.2 Baseline documentation of ‘target’ and ‘non-target’ lesions**

Where more than one measurable lesion is present at baseline all lesions up to a maximum of five lesions total (and a maximum of two lesions per organ) representative of all involved organs should be identified as *target lesions* and will be recorded and measured at baseline. For example, in instances where patients have only one or two organ sites involved, a maximum of two and four lesions respectively will be recorded). Target lesions should be selected on the basis of their size (lesions with the longest diameter), be representative of all involved organs, but in addition should be those that lend themselves to *reproducible repeated measurements*. It may be

the case that, on occasion, the largest lesion does not lend itself to reproducible measurement in which circumstance the next largest lesions which can be measured reproducibly should be selected.

*Lymph nodes* merit special mention since they are normal anatomical structures which may be visible by imaging even if not involved by tumor. As noted above, pathological nodes which are defined as measurable and may be identified as target lesions must meet criterion of a short axis of  $\geq 15$  mm by CT scan. Only the *short* axis of these nodes will contribute to the baseline sum. The short axis of the node is the diameter normally used by radiologists to judge if a node is involved by solid tumor. Nodal size is normally reported as two dimensions in the plane in which the image is obtained (for CT scan this is almost always the axial plane; for MRI the plane of acquisition may be axial, sagittal or coronal). The smaller of these measures is the short axis. For example, an abdominal node which is reported as being 20 mm x 30 mm has a short axis of 20 mm and qualifies as a malignant, measurable node. In this example, 20 mm should be recorded as the node measurement. All other pathological nodes (those with short axis  $\geq 10$  mm but  $< 15$  mm) should be considered non-target lesions. Nodes that have a short axis  $< 10$  mm are considered non-pathological and should not be recorded or followed.

A *sum of the diameters* (longest for non-nodal lesions, short axis for nodal lesions) for all target lesions will be calculated and reported as the *baseline sum diameters*. If lymph nodes are to be included in the sum, then as noted above, only the *short* axis is added into the sum. The baseline sum diameters will be used as reference to further characterize any objective tumor regression in the measurable dimension of the disease.

All other lesions (or sites of disease) including pathological lymph nodes should be identified as *non-target lesions* and should also be recorded at baseline. Measurements are not required and these lesions should be followed as ‘present’, ‘absent’, or in rare cases ‘unequivocal progression’. In addition, it is possible to record multiple non-target lesions involving the same organ as a single item on the case record form (e.g. ‘multiple enlarged pelvic lymph nodes’ or ‘multiple liver metastases’).

## 2.3 Response criteria

This section provides the definitions of the criteria used to determine objective tumor response for target lesions.

### 2.3.1 Evaluation of target lesions

*Complete Response (CR)*: Disappearance of all target lesions. Any pathological lymph nodes (whether target or non-target) must have reduction in short axis to  $< 10$  mm.

*Partial Response (PR)*: at least a 30% decrease in the sum of diameters of target lesions, taking as reference the baseline sum diameters.

*Progressive Disease (PD)*: at least a 20% increase in the sum of diameters of target lesions, taking as reference the *smallest sum on study* (this includes the baseline sum if that is the smallest on study). In addition to the relative increase of 20%, the sum must also demonstrate an

absolute increase of at least 5 mm. (*Note:* the appearance of one or more new lesions is also considered progression).

*Stable Disease (SD):* Neither sufficient shrinkage to qualify for PR nor sufficient increase to qualify for PD, taking as reference the smallest sum diameters while on study.

### **2.3.2 Special notes on the assessment of target lesions**

*Lymph nodes.* Lymph nodes identified as target lesions should always have the actual short axis measurement recorded (measured in the same anatomical plane as the baseline examination), even if the nodes regress to below 10 mm on study. This means that when lymph nodes are included as target lesions, the ‘sum’ of lesions may not be zero even if complete response criteria are met, since a normal lymph node is defined as having a short axis of < 10 mm. In order to qualify for CR, each node must achieve a short axis < 10 mm. For PR, SD and PD, the actual short axis measurement of the nodes is to be included in the sum of target lesions.

*Target lesions that become ‘too small to measure’.* While on study, all lesions (nodal and non-nodal) recorded at baseline should have their actual measurements recorded at each subsequent evaluation, even when very small (e.g. 2 mm). However, sometimes lesions or lymph nodes which are recorded as target lesions at baseline become so faint on CT scan that the radiologist may not feel comfortable assigning an exact measure and may report them as being ‘too small to measure’. When this occurs it is important that a value be recorded on the case report form. If it is the opinion of the radiologist that the lesion has likely disappeared, the measurement should be recorded as 0 mm. If the lesion is believed to be present and is faintly seen but too small to measure, a default value of 5 mm should be assigned (*Note:* It is less likely that this rule will be used for lymph nodes since they usually have a definable size when normal and are frequently surrounded by fat such as in the retroperitoneum; however, if a lymph node is believed to be present and is faintly seen but too small to measure, a default value of 5 mm should be assigned in this circumstance as well). This default value is derived from the 5 mm CT slice thickness (but should not be changed with varying CT slice thickness). The measurement of these lesions is potentially non-reproducible, therefore providing this default value will prevent false responses or progressions based upon measurement error. However, if the radiologist is able to provide an actual measure, that should be recorded, even if it is below 5 mm.

*Lesions that split or coalesce on treatment.* When non-nodal lesions ‘fragment’, the longest diameters of the fragmented portions should be added together to calculate the target lesion sum. Similarly, as lesions coalesce, a plane between them may be maintained that would aid in obtaining maximal diameter measurements of each individual lesions. If the lesions have truly coalesced such that they are no longer separable, the vector of the longest diameter in this instance should be the maximal longest diameter for the ‘coalesced lesion’.

### **2.3.3 Evaluation of non-target lesions**

This section provides the definitions of the criteria used to determine the tumor response for the group of non-target lesions. While some non-target lesions may actually be measurable, they need not be measured and instead should be assessed only *qualitatively* at the time points specified in the protocol.

*Complete Response (CR):* Disappearance of all non-target lesions. All lymph nodes must be non-pathological in size (< 10 mm short axis).

*Non-CR/Non-PD:* Persistence of one or more non-target lesions(s).

*Progressive Disease (PD): Unequivocal progression* (see comments below) of existing non-target lesions. (Note: the appearance of one or more new lesions is also considered progression).

### **2.3.4 Special notes on assessment of progression of non-target disease**

The concept of progression of non-target disease requires additional explanation as follows:

*When a patient also has measurable disease.* In this setting, to achieve ‘unequivocal progression; on the basis of the non-target disease, there must be an overall level of substantial worsening in non-target disease such that, even in presence of SD or PR in target disease, the overall tumor burden has increased sufficiently to merit discontinuation of therapy. A modest ‘increase’ in the size of one or more non-target lesions is usually not sufficient to qualify for unequivocal progression status. The designation of overall progression *solely* on the basis of change in non-target disease in the face of SD or PR of target disease will therefore be extremely rare.

*When the patient has only non-measurable disease.* The same general concepts apply here as noted above, *however*, in this instance there is no measurable disease assessment to factor into the interpretation of an increase in non-measurable disease burden. Because worsening in non-target disease cannot be easily quantified (by definition: if all lesions are truly non-measurable) a useful test that can be applied when assessing patients for unequivocal progression is to consider if the increase in overall disease burden based on the change in non-measurable disease is comparable in magnitude to the increase that would be required to declare PD for measurable disease: i.e. an increase in tumor burden representing an additional 73% increase in ‘volume’ (which is equivalent to a 20% increase diameter in a measurable lesion). Examples include an increase in a pleural effusion from ‘trace’ to ‘large’, an increase in lymphangitic disease from localized to widespread, or may be described in protocols as ‘sufficient to require a change in therapy’. If ‘unequivocal progression’ is seen, the patient should be considered to have had overall PD at that point. While it would be ideal to have objective criteria to apply to non-measurable disease, the very nature of that disease makes it impossible to do so; therefore, the increase must be substantial.

### **2.3.5 New Lesions**

The appearance of new malignant lesions denotes disease progression. There are no specific criteria for the identification of new radiographic lesions; however, the finding of a new lesion should be unequivocal: i.e. not attributable to differences in scanning technique, change in imaging modality or findings thought to represent something other than tumor (for example, some ‘new’ bone lesions may be simply healing or flare of pre-existing lesions). This is particularly important when the patient’s baseline lesions show partial or complete response. For example, necrosis of a liver lesion may be reported on a CT scan report as a ‘new’ cystic lesion, which it is not.

A lesion identified on a follow-up study in an anatomical location that was *not* scanned at baseline is considered a new lesion and will indicate disease progression. An example of this is the patient who has visceral disease at baseline and while on study has a CT or MRI brain ordered which reveals metastases. The patient's brain metastases are considered to be evidence of PD even if he/she did not have brain imaging at baseline.

If a new lesion is equivocal, for example because of its small size, continued therapy and follow-up evaluation will clarify if it represents truly new disease. If repeat scans confirm there is definitely a new lesion, then progression should be declared using the date of the initial scan.

## **2.4 Evaluation of best overall response**

The best overall response is the best response recorded from the start of the study treatment until the end of treatment taking into account any requirement for confirmation. The patient's best overall response assignment will depend on the findings of both target and non-target disease and will also take into consideration the appearance of new lesions.

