**Criteria for Evaluation:**

Safety Assessments:

The safety assessment will be based on the evaluation of adverse events (AEs) that occur from the time of initiation of administration of study drug through 30 days following the last dose of study drug or until the start of a subsequent systemic anticancer therapy (whichever occurs first) and will be determined based on signs, symptoms, physical examination findings, and/or laboratory test results from enrolled participants as appropriate. Progression of the underlying tumor resulting in hospitalization or death (e.g., participant hospitalized for or dies from progressive disease [PD]) will be documented as a tumor response and not as a serious adverse event (SAE).

Response Assessments:

Tumor assessments will be obtained using computed tomography (CT) or positron emission tomography/CT (PET/CT) and/or magnetic resonance imaging (MRI) scans. For mCRPC participants a bone scan will be obtained in addition to CT and/or MRI scans at baseline and on study. Target and non-target lesions will be designated at screening and then evaluated at every 6 weeks (42 days) for the first four cycles, and every other cycle thereafter while the participant in Module A Dose Escalation and Module B is on study treatment. Target and non-target lesions will be designated at screening and then evaluated every 9 weeks (63 days) while the participant is on study treatment in Cohort Expansion Phase for Module A. For mCRPC a lymph node is to be  $\geq 20$  mm to be a target lesion. In situations where the bone scan findings are suggestive of a flare reaction or apparent new lesion(s) may represent trauma, additional imaging to confirm these results with other imaging modalities such as MRI or fine-cut CT should be obtained. At each tumor assessment time point, the overall response status will be determined based on assessment of target and non-target lesions as well as appearance of any new lesions. For RECIST v1.1 ([Appendix 5](#)), the overall responses will be categorized as complete response (CR), partial response (PR), stable disease (SD), progressive disease (PD), or not evaluable (NE).

Survival Assessments:

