### **5.4 Rules for Study Treatment Discontinuation**

Participants who tolerate treatment may continue to receive treatment with the study drug(s) as specified in the protocol until any one of the following conditions are met:

- Participant meets RECIST v1.1 criteria for disease progression
- Participant meets PCWG-2 criteria for radiographic progression
- Withdrawal of participant due to an AE or SAE
- Withdrawal of participant consent
- Completion of protocol-defined therapy
- Investigator discretion
- Pregnancy
- Occurrence of drug-related DLT or AEs that lead to discontinuation of study drug
- Dose delay > 21 days due to AEs unless approved by the sponsor.
- The sponsor, investigator, or regulatory agency terminates the study
- Death

For individual participants who meet these criteria, but who are otherwise considered to be experiencing clinical benefit in the judgment of the investigator, consideration may be given to continue therapy of MGC018 alone (Module A) or in combination with MGA012 (Module B), for up to maximum of total of 18 cycles (i.e. approximately 2 years), on a case-by-case basis in consultation with the sponsor. If the investigator decides that the participant should be withdrawn from the study or from dosing for any reason other than

disease progression, the sponsor or its designee must be alerted within 24 hours by completing the appropriate electronic case report forms (eCRFs) ([Section 12.2.2](#)).

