5 ENDPOINTS

5.1 Efficacy Endpoints

5.1.1 Response Endpoints

Response by RECIST v1.1: The best overall response (BOR) will be categorized as complete response (CR), partial response (PR), stable disease (SD), progressive disease (PD), or not evaluable (NE). To be qualified as BOR, CR and PR require confirmation at least 4 weeks after initial observation of such response, and SD requires to be observed at least once after 6 weeks from the start of MGC018 treatment for Module A or MGC018 and MGA012 combination treatment for Module B.

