5.1.2 Time-to-event Endpoints

- PFS: PFS is defined as the time from the first dose date of MGC018 treatment (Module A) or MGC018 and MGA012 combination treatment (Module B) to the date of first documented progression or death from any cause, whichever occurs first. The documented progression is determined by radiographic assessment using RECIST v1.1. PFS will be calculated as:

$$\text{PFS (months)} = (\text{date of event [documented progression or death] or date of censoring} - \text{first dose date} + 1) / (365.25/12)$$

- Duration of response (DoR): DoR is defined as the time from the date of initial response (CR or PR) to the date of first documented progression or death from any cause, whichever occurs first. DoR is calculated only for the responders (i.e., participants who have CR or PR). The documented progression is determined by radiographic assessment using RECIST v1.1. DoR will be calculated as:

$$\text{DoR (months)} = (\text{date of event [documented progression or death] or date of censoring} - \text{date of initial response} + 1) / (365.25/12)$$

- OS: OS is defined as the time from the first dose date of MGC018 treatment for Module A or MGC018 and MGA012 combination treatment for Module B to the date of death from any cause. OS will be calculated as:

$$\text{OS (months)} = (\text{date of death or last known alive} - \text{first dose date} + 1) / (365.25/12)$$

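### The best overall response window runs to end of treatment and is not closed at first progression, so a confirmed response after RECIST progression would count in ORR and leave its duration negative or ambiguous

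*Protocol*

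**What the plan says.** **BOR window.** Appendix 5, section 2.4 of the Protocol: "The best overall response is the best response recorded from the start of the study treatment until the end of treatment", qualified only by any confirmation requirement. SAP 5.1.1 adds that "To be qualified as BOR, CR and PR require confirmation at least 4 weeks after initial observation of such response", plus a minimum of 6 weeks for stable disease. Protocol 14.6.1 says the same. Neither names first progression as the end of the window. SAP 6.7.1 then counts every BOR of CR or PR in the response evaluable population as a response.

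**Treatment past progression.** Protocol 5.4 lists "Participant meets RECIST v1.1 criteria for disease progression" among the reasons to stop study drug. The same section makes an exception: "For individual participants who meet these criteria, but who are otherwise considered to be experiencing clinical benefit in the judgment of the investigator" may be considered for continued therapy, after consulting the sponsor, within the 18-cycle maximum.

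**Scans continue.** In the Synopsis, lesions are "evaluated every 9 weeks (63 days) while the participant is on study treatment in Cohort Expansion Phase for Module A". The other parts of the study are scanned every 6 weeks for four cycles, then every other cycle, also while on treatment.

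**Partial response.** Appendix 5, section 2.3.1 requires "at least a 30% decrease in the sum of diameters of target lesions, taking as reference the baseline sum diameters". The reference is baseline, so earlier progression does not rule it out.

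**Duration of response.** SAP 5.1.2 defines it as "time from the date of initial response (CR or PR) to the date of first documented progression or death from any cause", for all responders. It does not say that the progression must follow the response.

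**The concern.** The BOR window and the continuation rule do not fit together. The first runs to end of treatment; the second lets treatment run on after progression. A participant can therefore progress, stay on drug, shrink to 30% below baseline on two scans at least 4 weeks apart, and be reported as a responder.

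Three consequences follow.

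- ORR and PFS would describe different stretches of the same participant's treatment, because the PFS event precedes the response.
- DoR has no clear value for that participant.
- The effect runs one way. Extending the window of a best response can only keep or raise it, and it can do so only for participants whom the investigator chose to keep on an open-label drug.

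The plan does set limits after other events. Protocol 8.1.1 ends evaluability for objective response once palliative radiotherapy overlaps target lesions, and PFS is censored when alternative anti-cancer treatment starts. BOR has no matching rule for progression. The best percent change in tumor size (SAP 5.1.3 and 6.7.4) has no stated end either.

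Antitumor activity by RECIST v1.1 is a secondary objective, and Protocol 14.1 sizes the tumor-specific cohorts mainly on estimating responses.

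**Working it through.** **1. The plan's own figures.** Protocol Table 10 and SAP Table 1 give exact 95% intervals for 1 to 6 responses in 16. Clopper-Pearson limits reproduce all six rows, including:

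- 2/16 = 12.5% (1.6 to 38.3)
- 3/16 = 18.8% (4.0 to 45.6)
- 4/16 = 25.0% (7.3 to 52.4)

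**2. A path through the rules.** The target-lesion sums (mm) are assumed for illustration. Scans are every 63 days, as in Module A expansion, and the first dose is on Day 1.

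| Day | Sum | Rule applied | Time-point response |
|---|---|---|---|
| Baseline | 100 | reference | |
| 63 | 125 | at least 1.2 × 100 = 120, and a rise of at least 5 mm | PD |
| 126 | 65 | at most 0.7 × 100 = 70 | PR |
| 189 | 60 | at most 70; 63 days after the first PR, more than 4 weeks | PR, confirmed |

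BOR to end of treatment is PR, and the participant counts in ORR. BOR cut at first progression is PD. Best percent change is (60 - 100)/100 = -40% as written, and (125 - 100)/100 = +25% with the cut.

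**3. PFS for this participant.** (63 - 1 + 1)/(365.25/12) = 63/30.4375 = 2.07 months. The response starts on Day 126, after that event.

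**4. DoR by the literal SAP formula**, (first progression - initial response + 1)/30.4375:

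- 9-week scans, PD Day 63, PR Day 126: (63 - 126 + 1)/30.4375 = -2.04 months
- 9-week scans, PR one scan later, Day 189: (63 - 189 + 1)/30.4375 = -4.11 months
- 6-week scans, PD Day 42, PR Day 84: (42 - 84 + 1)/30.4375 = -1.35 months
- 6-week scans, PR one scan later, Day 126: (42 - 126 + 1)/30.4375 = -2.73 months

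The last three rows of SAP Table 2, which SAP 6.7.2.2 applies to DoR, do not cover progression before response.

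**5. DoR on the other reading.** Appendix 5, section 2.5.2 can be taken to mean the next progression after the response. If that came on Day 252 (assumed), DoR = (252 - 126 + 1)/30.4375 = +4.17 months, in a participant whose PFS ended at 2.07 months.

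**6. Effect on ORR.** Each post-progression responder adds 1/16 = 6.25 points. The documents do not say how many to expect, so 0 to 2 of 16 is an assumed range.

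| Responders as written | Of whom post-progression | ORR as written | ORR with the cut |
|---|---|---|---|
| any | 0 | unchanged | unchanged |
| 3 | 1 | 18.8% (4.0 to 45.6) | 12.5% (1.6 to 38.3) |
| 4 | 2 | 25.0% (7.3 to 52.4) | 12.5% (1.6 to 38.3) |

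**The case against.** The strongest reply is that Appendix 5 as a whole implies the conventional rule. Section 2.5.3 measures stable disease only until progression, and Table A-2 shows PD only as the subsequent time point, never the first. That is fair as to intent. But Table A-2 leaves the case unsettled, and section 2.4 states a window that contradicts the implied rule.

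Four stronger readings are tempting, and the documents do not support them.

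- **That DoR must be negative.** This follows only from the literal SAP formula. Appendix 5, section 2.5.2 allows a forward interval. What stands is that the SAP does not choose.
- **That PD is upgraded to SD when lesions merely return toward baseline.** Section 2.5.3 points against this, so only later PR or CR is at issue.
- **That any progression can be overwritten.** Under Table A-1 a time point with a new lesion is PD, so that route is generally closed. Appendix 5 calls progression solely on non-target disease, despite SD or PR in target lesions, extremely rare. An equivocal finding that is not later confirmed is not progression, so a later response there is ordinary. The affected set is mainly target-lesion growth.
- **That every expansion cohort rests on ORR.** The mCRPC expansion is sized primarily on the 6-month rPFS rate, although ORR and DoR are still reported there (Protocol 14.6.4).

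It is also true that ORR is descriptive here, with no test or threshold attached, and that spider plots would show late shrinkage. Neither settles who is counted as a responder. The separate programming plan was not available and may contain a cut-off. SAP section 7 gives it output shells, reporting conventions and programming specifications; an endpoint definition belongs in the SAP.

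**Conclusion.** The concern holds in a limited form. Following the plan literally, a participant with progression from target-lesion growth (rarely, non-target disease) and a later confirmed PR against baseline is a responder in ORR with a PFS event before the response. Two programmers could defensibly report different DoR values for that participant.

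The size is 6.25 points of ORR per such participant in a cohort of 16, assuming all 16 are response evaluable. The number may be zero: progression is a listed stopping criterion, continuation is an exception, and a confirmed response afterwards is needed. A reader might infer that ORR will be inflated. The documents show only that it could be, and in which direction.

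This is more than missing detail, because the stated window itself gives the unconventional classification under a continuation rule that the same plan provides.

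**What to change.** In SAP 5.1.1 and Appendix 5, section 2.4, state that BOR is derived from assessments up to and including the first documented RECIST v1.1 progression, or the start of subsequent anti-cancer therapy if that is earlier. Apply the same cut to best percent change in SAP 5.1.3 and 6.7.4. List any post-progression response separately, outside ORR and DoR. This also removes the DoR ambiguity, since no responder would then have progression before response.

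The subsequent-therapy part is largely redundant, because BOR already ends with treatment and Protocol 8.1.1 prohibits other anti-cancer therapy on study. It does no harm.

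The cost is one definition, a matching line for best percent change, and one listing. ORR may be slightly lower. No change to the treatment-continuation rule in section 5.4 is implied.
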